DRFs are a prime target for generic implant implementation, due to the relatively high incidence of DRFs (634,000 annually) (Mauk Orthop Clin North America 2018), and the substantial amount spent by Medicare each year on DRF management (\$385-\$535 million) (Ray JBMR 1997, Burge JBMR 2007). The purpose of this study was to assess for differences in implant cost, surgical characteristics, and 90-day clinical outcomes between patients treated with generic volar locking plates (VLPs) and conventional VLPs in the setting of a DRF. We hypothesized that there would be no difference in surgical characteristics (e.g., tourniquet times) or clinical outcomes (e.g., reoperation), however there would be reduced cost in the generic VLP group.

4. Approach

a. Study design

- i. This will be a prospective randomized controlled trial within Healthpartners in the greater Minneapolis area in Minnesota, to compare primary outcomes of subjects between generic and conventional volar locking plates in distal radius fracture patients. Group selection will be randomized month to month with generic plates being used one month and conventional plates the next.

i. Inclusion

1. >18 years old
2. Isolated DRF
3. Medical need for surgical fixation with a volar locking plate

ii. Exclusion

1. No VLP used
2. Additional fixation used
3. Injury was non-isolated (polytrauma)
4. < 18 years old
5. Open fracture

- b. Data collection process
 - i. Identify patients within HealthPartners who meet inclusion criteria who are determined to need distal radius ORIF
 - 1. Patients meeting inclusion criteria will be identified by the included surgeons on the study
 - ii. Consent
 - 1. Written informed consent for surgery will be obtained by the attending surgeon, however no additional consent will be needed as this is an FDA approved device
 - iii. Data sources needed for this study
 - 1. Chart Review for patient age, gender, height and weight
 - 2. Chart review for mortality, reoperation, readmission
 - 3. Chart review for implants, tourniquet time, estimated blood loss
 - 4. Implants will be cross referenced with institutional charge master database to obtain cost.
 - iv. Process steps for data acquisition
 - 1. Data to be obtained by chart review after completion of the study.
- c. Intervention, treatments
 - i. Patients will be randomized by month with patients during one month receiving generic implants and the following month they receive conventional implants.

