 - ii. All other standards of care remain equal between the groups.
- d. *Outcomes/endpoint and other variable definitions, and instruments used*
 - i. 90-day reoperation
 - ii. 90-day readmission
 - iii. 90-day mortality
 - iv. Implant cost
 - v. Estimated blood loss
 - vi. Tourniquet Time
- e. *Statistical analysis plan*
 - i. T-Tests and Chi-square of Demographic Data
 - ii. Chi-square of primary outcomes
 - 1. 90-day reoperation rate
 - 2. 90-day readmission rate
 - 3. 90-day mortality rate
 - iii. T-Test of Secondary Outcome Measures between subject groups
 - 1. Implant cost
 - 2. Tourniquet time
 - 3. Estimated blood loss
 - iv. Power analysis or statement of precision
An a priori power analysis was conducted to estimate the minimum sample size needed to adequately detect a difference in reoperation rates with a large effect size (Cohen's $d=0.8$). At a Type I error rate of 0.05, a power of 80%, and a 1:1

group allocation, the estimated sample size was 36 patients (18 generic VLPs vs. 18 conventional VLPs).

v. Strengths

1. Blinding of patients
2. Use of FDA approved devices
3. Randomizing of patients
4. Adequate qualified staff members to conduct the study
5. Surgeons will be adequately trained and reminded on the protocol and their specific research related duties.
6. High-volume surgeons who regularly treat distal radius fractures
7. Conservative effect size estimates

vi. Limitations

1. Surgeons are not blinded
2. Only early follow-up (90 days)
3. No patient reported outcomes included

5. Setting/Environment/Organizational feasibility

- a. This study will be conducted at Healthpartners within Minneapolis metropolitan area
- b. This HealthPartners setting has an appropriate patient population to carry out the proposed study.
- c. The orthopedic department leadership has been engaged in development and approval of this study

6. Risks and Benefits

- a. Potential risks
 - i. No different than associated risks of undergoing a standard DRF ORIF.
- b. Benefit to society
 - i. Being able to validate the use of cheaper implants to save cost for patients and healthcare systems.

7. Data Confidentiality and Privacy

- a. In order to secure patient confidentiality and data security, all data will be de-identified. All patients will be assigned a research identification number (not their MRN) that cannot be associated with their name, birthdate, or other identifying information.

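### Two exclusions depend on what was used at surgery, after the month has set a plate the surgeon knows, and no analysis set is named; applied as written, they can remove patients unequally by arm

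*Combined protocol and SAP*

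**What the plan says.** Assignment is by calendar month (4.a, Study design): "Group selection will be randomized month to month with generic plates being used one month and conventional plates the next". The limitations in 4.e.vi include "Surgeons are not blinded".

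The exclusion list in 4.a contains two items that describe the operation: "Additional fixation used", and the item that removes patients in whom no VLP was used. The third inclusion criterion, by contrast, is worded as a medical need for a VLP.

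Under 4.b.i the participating surgeons identify patients who meet the inclusion criteria and need fixation. That line does not mention the exclusions. Section 4.b.iii lists "Chart review for implants, tourniquet time, estimated blood loss" as a source, and separately chart review for mortality, reoperation and readmission. On timing, 4.b.iv says "Data to be obtained by chart review after completion of the study".

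Section 4.e lists t-tests, chi-square tests and a sample size of 36 (18 per arm). It defines no analysis set, no handling of a plate that differs from the month's plate, and no reporting of exclusions by arm. The primary aims in section 2 compare patients by the plate they were treated with.

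**The concern.** Whether extra fixation is added, or a VLP is used at all, is decided by a surgeon who already knows the month's plate. Excluding on that basis conditions the comparison on an event after assignment. If added fixation or a no-VLP operation is more frequent in one arm, or is chosen for different fractures, the patients who remain are no longer comparable.

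Reoperation, tourniquet time, blood loss and implant cost could then be biased in either direction. Readmission and mortality would be affected only if their risk also depends on fracture difficulty. Unlike sampling error, this bias does not shrink with more patients and does not show in a p-value or confidence interval. Without counts by arm, a reader cannot judge it.

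There is also a loss of information. If one plate more often needed added fixation, that would bear on the wider adoption that section 1 has in view. Yet those patients are removed, their extra implants leave the cost comparison, and no endpoint in 4.d records the event.

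**Working it through.** The plan gives no exclusion rate or event rate, so there is no figure of its own to reproduce on this point. The 18 per arm is taken from 4.e.iv as a scale only; whether 36 is the right total is a separate question. **All rates below are assumptions.**

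**Scale.** One patient in 18 is 1/18 = 5.6 points.

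**False difference when the plates truly do not differ.** Let h be the share of hard fractures and f the share of those removed by the exclusions. The hard share left is h' = h(1−f)/(1−hf). Assume reoperation risk is 25% in hard fractures and 3% in the rest. The analysed rate is then 0.03 + 0.22h'. With h = 0.20 the true rate is 0.20×0.25 + 0.80×0.03 = 7.4% in both arms. With f = 0.25 in the conventional arm, h' = 0.15/0.95 = 0.158 and its analysed rate is 6.5%.

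| f, generic | h', generic | Generic rate | Shift (points) | Patients (of 18) |
|---|---|---|---|---|
| 1.00 (extreme) | 0 | 3.0% | −3.5 | 0.6 |
| 0.75 | 0.05/0.85 = 0.059 | 4.3% | −2.2 | 0.4 |
| 0.50 | 0.10/0.90 = 0.111 | 5.4% | −1.0 | 0.2 |
| 0.25 | 0.158 | 6.5% | 0 | 0 |

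With h = 0.10 the first three shifts are −1.7, −1.1 and −0.5 points. Swapping the arms reverses the sign.

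A milder gap in risk (2% and 15%, h from 0.10 to 0.30) gives 0.3 to 0.9 points for 50% against 25% removed, and 0.8 to 2.3 points for 80% against 20%. The largest of these is 0.023×18 = 0.4 of a patient.

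**Standard error at 18 per arm.** For 3.0% against 6.5%: √(0.030×0.970/18 + 0.0647×0.9353/18) = 7.1 points. For 5.4% against 6.5% it is 7.9 points.

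**True difference hidden.** Suppose 20% of the generic arm and 5% of the conventional arm need added fixation, at 25% risk, with 3% otherwise. The rates are 0.20×0.25 + 0.80×0.03 = 7.4% and 0.05×0.25 + 0.95×0.03 = 4.1%, a difference of 3.3 points (0.6 of a patient; standard error 7.7). After exclusion it is 3% against 3%, or zero. That zero follows from assuming equal risk in the plate-only patients.

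**Tourniquet time.** If hard fractures take 1 SD longer, the shift is the difference in h'. It is 0.16 SD for 100% against 25% removed and 0.111 − 0.158 = −0.05 SD for 50% against 25%. The standard error is √(2/18) = 0.33 SD. Blood loss follows the same formula under the same assumption.

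**Implant cost.** Set the conventional plate at 1, the plate-only saving at s, and added fixation at x per patient who receives it. With added fixation in 20% of generic and 5% of conventional patients, the all-implant saving is 1 − [(1−s) + 0.20x]/(1 + 0.05x). The documents give no saving for VLPs. The 49% and 73% in section 3 refer to orthopaedic trauma procedures and are used only as a range, with 20% added.

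| s | x = 0.25 | x = 1 |
|---|---|---|
| 20% | 16.0% | 4.8% |
| 49% | 44.7% | 32.4% |
| 73% | 68.4% | 55.2% |

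The sign reverses only if s is below 0.15x, that is 3.75% at x = 0.25 or 15% at x = 1. If the 20% and 5% are swapped, the all-implant saving exceeds the plate-only one: at s = 49% and x = 1 it is 1 − 0.56/1.20 = 53.3%.

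**The case against.** **The criteria may describe plans.** The same list says "Injury was non-isolated (polytrauma", a pre-operative fact in the past tense, and 4.b.i places identification by surgeons at the point where fixation is judged necessary. This reading is open. It does not remove the problem, because the wording is not limited to plans and a surgeon who knows the month's plate also plans with that knowledge.

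**The question is plate against plate.** The aims compare patients by the plate they were treated with, and a VLP-only set fits that. This stands as a reason to keep the plate-only analysis at full weight. It does not name an analysis set.

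**Care is the same in both arms.** Section 4.c states "All other standards of care remain equal between the groups", and section 1 says many surgeons have no brand preference. Section 3, however, reports surgeon concern about the quality and safety of generic implants. None of this rules unequal removal in or out.

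**Cost is largely covered.** Implants are already taken from the chart and matched to the charge master, and the cost aim can be read as plate against plate. That is fair; what is missing is the cost in the excluded patients.

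**The effect is below noise.** This stands for a single trial of this size: every modelled reoperation shift is under one patient, on assumed rates. A reader might infer that exclusions will be decided after outcomes are known, since one chart review supplies both. The text permits that but does not say that eligibility is settled then.

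**Conclusion.** The structural gap is in the text: two exclusions worded by use, a plate set beforehand and known to the surgeon, no stated time for applying the exclusions, and no named analysis set or count by arm. Followed as written, the plan can condition the comparison on an event after assignment.

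The impact is uncertain and may be small. On the assumed rates, the reoperation shift runs from 0 to 3.5 points (at most 0.6 of a patient at 18 per arm) against a standard error of 7 to 8 points. The tourniquet-time shift is 0.05 to 0.16 SD against 0.33 SD. For cost, the size of the saving is more at stake than its sign.

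The documents do not support the stronger inferences that removal is unequal, that it favours the generic plate, or that it would overturn the result. Equal removal of comparable patients would narrow the population without biasing the reoperation comparison. The point merits correction because the remedy is cheap and the bias cannot otherwise be seen.

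**What to change.** - Define eligibility by pre-operative facts already in the criteria: adult, isolated closed distal radius fracture, need for VLP fixation.
- Analyse all eligible patients by the plate assigned to their month, whatever was implanted. The SAP should say which date fixes the month.
- Show the plate-only set alongside, with equal prominence. The hypothesis is no difference in clinical outcomes, and the assigned-month analysis can dilute towards that result, so neither set should stand alone.
- Report no-VLP, added-fixation and switched-plate cases by arm, with reasons.
- Give implant cost both for all implants used and for the plate only.
- Report the number of eligible patients per month.

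The cost is protocol and SAP wording plus slightly more chart review, since the charts are already being read. The statistical downside is some dilution of the plate-versus-plate contrast. The change does not stop a surgeon who knows the month from judging the need for a VLP differently; the monthly counts help to show that but do not prevent it.

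### Unblinded surgeons who know the month's plate are the only stated route into the trial, and nothing checks that they identify every eligible operated case

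*Combined protocol and SAP*

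**What the plan says.** All references are to the combined protocol and SAP.

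- **Entry (4.b.i.1):** "Patients meeting inclusion criteria will be identified by the included surgeons on the study". No other route is described. The line above it speaks of identifying HealthPartners patients who meet the criteria and need distal radius ORIF.
- **Allocation (4.a):** "Group selection will be randomized month to month with generic plates being used one month and conventional plates the next". Section 4.c.i repeats this: "patients during one month receiving generic implants and the following month they receive conventional implants".
- **Blinding:** 4.e.v lists "Blinding of patients" as a strength; 4.e.vi lists "Surgeons are not blinded" as a limitation.
- **Eligibility (4.a):** age and isolated injury are facts of the record, as is the open-fracture exclusion. The third inclusion criterion, "Medical need for surgical fixation with a volar locking plate", is a clinical judgement.
- **Consent (4.b.ii):** beyond surgical consent, "no additional consent will be needed as this is an FDA approved device".
- **Data (4.b.iii and 4.b.iv):** "Data to be obtained by chart review after completion of the study". The patient characteristics named are age, gender, height and weight.
- **Analysis (4.e.i to 4.e.iii):** t-tests and chi-square tests on demographics, unadjusted chi-square for the three primary outcomes, and t-tests for cost, tourniquet time and blood loss.

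**The concern.** Selection into a trial is harmless to the comparison when it happens without knowledge of the arm. Here the month fixes the arm, and the person who brings the patient in can know it. If the harder fractures are reported less completely in months with one of the plates, the two groups are no longer comparable samples of the same surgeons' cases.

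The outcomes most exposed are reoperation, readmission, tourniquet time and blood loss. Direction also matters. Section 3 hypothesises no difference in clinical outcomes, and fewer hard cases in generic months would flatter the generic plate or hide a true disadvantage. Adjustment cannot repair this, because a patient who was never identified has no data in the analysis.

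**Working it through.** **1. Can the arm be known before identification?** The documents do not say so in one sentence. It follows from two statements: plates alternate by month (4.a, 4.c.i), and surgeons are unblinded (4.e.vi). Once one month's plate is known, the later ones follow. Patient blinding does not help, because patients do not decide who is identified.

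**2. Is completeness checked?** The plan contains no rule for consecutive cases, no independent screener, no screening log and no count of eligible patients not identified. The chart review is described as a source of data on trial patients, not as a way of finding missed ones.

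**3. How large could the effect be?** The plan gives no event rates, so every input here is an assumption. Suppose there is no plate effect, 30% of fractures are complex, reoperation risk is 12% (complex) and 3% (simple), and mean tourniquet time is 90 and 60 minutes. Let f be the fraction of complex cases identified in generic months, with all cases identified in conventional months.

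- Complex share = 0.3f / (0.7 + 0.3f)
- Reoperation = 0.03 + 0.09 × share
- Tourniquet time = 60 + 30 × share

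| f | Complex share | Reoperation | Tourniquet (min) |
|---|---|---|---|
| 1.0 | 0.30/1.00 = 30.0% | 5.70% | 69.0 |
| 0.8 | 0.24/0.94 = 25.5% | 5.30% | 67.7 |
| 0.5 | 0.15/0.85 = 17.6% | 4.59% | 65.3 |

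Against complete identification, the spurious differences are 0.4 percentage points and 1.3 minutes at f = 0.8, and 1.1 points (ratio 4.59/5.70 = 0.81) and 3.7 minutes at f = 0.5.

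**4. Range under other assumptions.** Take a high-risk share of 20% to 40%, event risk of 10% to 20% in high-risk patients and 2% in others, again with no plate effect. Leaving out 25% of high-risk patients in generic months gives an apparent risk ratio (generic/conventional) of 0.86 to 0.91. Leaving out 50% gives 0.71 to 0.80. The largest absolute shift in that range is 9.2% to 6.5%, or 2.7 points.

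**5. Comparison with sampling error at the planned 18 per arm (4.e.iv).**

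- Reoperation at 5.7%: SE of the difference = √(2 × 0.057 × 0.943 / 18) = 7.7 points, against a bias of 1.1 points. In events, 18 × 0.011 = 0.2 reoperations.
- Reoperation at 9.2%: √(2 × 0.092 × 0.908 / 18) = 9.6 points, against 2.7 points.
- Tourniquet time, assuming an SD of 20 minutes: 20 × √(2/18) = 6.7 minutes, against 3.7 minutes.

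**6. Would the baseline tests show it?** Fracture type or severity is not among the variables listed, so a difference in difficulty could appear only indirectly, for example through age. At 18 per arm, power is about 31% for a standardised difference of 0.5 and 14% for 0.3. Even if severity were recorded, a high-risk share of 40% versus 25% would be detected with about 16% power. That is the 50% omission case at a 40% share: 0.20/0.80 = 25%.

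**The case against.** The case on the other side has several parts.

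- **The text requires identification.** A reader might infer that the plan lets surgeons pick whom to enter. It does not: it says patients meeting the criteria will be identified, and 4.e.v says surgeons will be trained and reminded of their research duties. Leaving out an eligible patient would depart from the plan, except where medical need leaves room for judgement. This stands. The gap is the absence of a check, not a licence to select.
- **Omissions could be found.** A reader might infer that a missed case would leave no trace. Operative records would show any operated case; the plan simply does not use them for this. Isolated injury is likewise a chart fact. Both points stand, and both make the fix easier.
- **The motive is uncertain.** Section 1 says many surgeons have no brand preference and that some in this system already use the generic plate. Section 3 does report concern among surgeons about quality and safety, and 26% use in one survey. Selection is possible; nothing shows that it occurs.
- **The cause is the monthly allocation.** With concealed individual allocation after entry, identification could not differ by arm. That is correct. But while allocation stays by month, completeness of identification needs its own safeguard.
- **The bias is small on invented inputs.** This stands for a trial of 36. It is not a reason to leave the gap, because this bias does not shrink with more patients and, without a denominator, no reader could rule it out.

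**Conclusion.** The point holds as a gap in safeguards. The only stated route into the trial runs through unblinded surgeons who can know the month's plate, and nothing in the plan verifies that eligible operated cases are all captured in both kinds of month. That they know the plate in advance is an inference, but a firm one.

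The size of any bias is unknown. In the illustrations, the reoperation shift is at most 2.7 percentage points against a standard error of 9.6, and the tourniquet shift is a little over half a standard error (3.7/6.7 = 0.56, with the SD itself assumed). A reader might infer that the trial's result is therefore invalid, or that selection would decide it; the documents do not support that. No figure can be put on the effect on implant cost. The reason to act is that the remedy costs little and the planned data would be unlikely to expose the problem.

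**What to change.** Replace 4.b.i.1 with text along these lines:

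> All consecutive distal radius ORIF cases performed by participating surgeons between the start and close of enrolment will be listed from the operative schedule or procedure records. A chart reviewer will apply the criteria on age, isolated injury and closed fracture from the pre-operative record, with plate and surgery date masked where practical. Nomination by the surgeon is not required. The numbers listed, eligible and not included, with reasons, will be reported by plate month.

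The cost is one protocol change, a query of operative records and a slightly longer list to screen. It fits within the chart review already planned. No trial consent is sought, so no patient contact is added, and the list can be built after enrolment closes.

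State the remaining limitation in 4.e.vi. A list of performed operations already depends on the surgeon's decision that a volar locking plate was needed and on the date chosen for surgery. The change therefore does not remove selection through that decision or through surgery moved across a month boundary. Monthly counts would only make large imbalances visible. Masking will also be imperfect, since the surgery date reveals the month.

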August 16, 2022

Do Generic Volar Locking Plates Provide Similar Outcomes at a Reduced Cost?

Study Protocol and Statistical Analysis Plan

Study Narrative

1. Summary

Distal radius fractures are a common injury in the community. When treated with open reduction internal fixation (ORIF), the volar locking plate (VLP) is the most frequent implant used. Current literature has shown most orthopaedic surgeons are unfamiliar with construct costs. Many surgeons use implants the hospital provides and have no preference for one implant company's plate over another. Previous studies have demonstrated increased implant costs do not increase patient reported outcomes (PROs) in other injury patterns. Generic implants can potentially reduce total procedural costs and not negatively impact patient outcomes. With an increasing emphasis being placed on providing high-value care to patients, and rising healthcare costs, there is a need to pursue more economical means of treating distal radius fractures. Additionally, with the increasing volume of distal radius fractures with a growing elderly population, it is important to consider adoption of an already partially implemented process. Some surgeons today in our health system use the generic VLP, with little apparent differences in reoperation rates and complications. Validation of its safety and efficacy on a larger scale could support its adoption as a universal stand of practice, thus reducing cost to the patient and hospital.

2. Study aims:

- a. Primary:
 - i. To determine if there is any difference in 90-day reoperation rate between patients treated with a generic or conventional volar locking plate.
 - ii. To determine if there is any difference in 90-day readmission rate between patients treated with a generic or conventional volar locking plate.
 - iii. To determine if there is any difference in 90-day mortality rate between patients treated with a generic or conventional volar locking plate.

- b. Secondary:
 - i. To determine if generic implants have a lower cost than conventional implants.
 - ii. To determine any differences in estimated blood loss by implant type (generic vs. conventional).
 - iii. To determine tourniquet time by implant type (generic vs. conventional).

3. Background, Rationale, Significance

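### All three primary outcomes rest on chart review alone, with no last-contact date and no rule for unknown 90-day status, and the timeline leaves late enrolees short of 90 days

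*Combined protocol and SAP*

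**What the plan says.** - **Source.** Section 4.b.iii lists "Chart review for mortality, reoperation, readmission" and names no other source for these outcomes: no call, visit, claims file or death register. The other chart items are demographics, implants, tourniquet time and blood loss. Date of last contact is not among them.
- **Timing.** Section 4.b.iv says "Data to be obtained by chart review after completion of the study". Section 8 closes enrolment in April 2023 and puts data analysis in May 2023.
- **Population.** Section 4.b.i is to "Identify patients within HealthPartners who meet inclusion criteria who are determined to need distal radius ORIF". Care received elsewhere is not mentioned.
- **Definitions.** Section 4.d gives labels only, such as "90-day readmission". It does not say what establishes that a patient was event-free at day 90.
- **Analysis.** Section 4.e.ii is "Chi-square of primary outcomes", with no rule on denominators, missing status or censoring. The limitations in 4.e.vi do not mention outcome capture.
- **Hypothesis.** Section 3 expects no difference in clinical outcomes, and no equivalence or non-inferiority margin is set.

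**The concern.** A chi-square test needs a yes or no for every patient analysed. The planned fields record events when they are found, but nothing that shows how long a patient was observed. A reviewer who finds no entry therefore cannot tell an event-free patient from one who was not observed to day 90. The analyst could not repair this later without going back to the charts for another field.

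This matters more than usual because the hoped-for result is a null one. Section 1 wants the study to support wider adoption of the generic plate, and with no margin set, a non-significant test will be read as support. Events that go unrecorded equally in both arms make that result more likely. The 90-day rates themselves would also be too low, and nobody could say by how much.

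**Working it through.** **The plan's own figures.** The documents give no event rate, capture rate or loss rate, so there is no ascertainment figure to reproduce. The only relevant number is the 18 per arm in 4.e.iv. It does not reproduce from its stated inputs: d = 0.8, alpha 0.05 and 80% power give 2 × (1.960 + 0.842)² / 0.8² = 24.5, so 25 per arm two-sided, and 20 per arm one-sided. That is a separate matter. Here 18 is used only as the arm size.

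**1. Equal capture.** Let a fraction c of true events be recorded in both arms. The observed difference is c·p₁ − c·p₂ = c(p₁ − p₂). The risk ratio, c·p₁ / c·p₂, is unchanged in expectation. The rates below are assumed. Power is by exact enumeration of the uncorrected chi-square test at 18 vs 18.

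| Events missed in both arms | 20% vs 5%: difference, power | 10% vs 5%: difference, power |
|---|---|---|
| 0% | 15 points, 25% | 5 points, 4% |
| 20% | 12 points, 18% | 4 points, 3% |
| 30% | 10.5 points, 14% | 3.5 points, 2% |
| 50% | 7.5 points, 6% | 2.5 points, 1% |

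**2. Unequal capture (assumed rates).**
- True rates of 10% in both arms, 30% missed in the generic arm only: 7% − 10% = −3 points, a false advantage for generic.
- True 10% generic vs 5% conventional, 30% missed in the conventional arm only: 10% − 3.5% = 6.5 points, wider than the true 5.

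**3. One missed event.** At 18 vs 18, chi-square = 36(ad − bc)² / (product of the four margins).
- 4 vs 0: 36 × (4 × 18)² / (18 × 18 × 4 × 32) = 4.50, p = 0.034.
- 3 vs 0: 36 × (3 × 18)² / (18 × 18 × 3 × 33) = 3.27, p = 0.070.

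Fisher's exact test gives the same sensitivity one event higher: 5 vs 0 is p = 0.046 and 4 vs 0 is p = 0.104.

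**4. Timeline.** Taking enrolment as 1 October 2022 to 30 April 2023 gives 31 + 30 + 31 + 31 + 28 + 31 + 30 = 212 days.
- Analysis on 31 May: 90 days earlier is 2 March. Surgery on 3 March to 30 April falls short: 29 + 30 = 59 days, and 59/212 = 28%.
- Analysis on 1 May: 90 days earlier is 31 January. February to April falls short: 28 + 31 + 30 = 89 days, and 89/212 = 42%.
- Surgery on 30 April reaches day 90 on 29 July 2023.

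If months strictly alternate from October, one arm has October, December, February and April (31 + 31 + 28 + 30 = 120 days) and the other has November, January and March (30 + 31 + 31 = 92 days). With analysis on 1 May, the short days are 58/120 = 48% and 31/92 = 34%. With analysis on 31 May, they are 30/120 = 25% and 29/92 = 32%. The shortfall is unequal between arms, and which arm is worse depends on the analysis date.

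**The case against.** Several stronger readings are tempting, and the documents do not support them.

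- **A reader might infer that the plan scores a missing entry as no event.** It states no such rule. Leaving patients of unknown status out of the test is equally compatible with 4.e.ii. What stands is that neither rule is written and that the listed fields would not identify those patients.
- **A reader might infer that missed events must push the result towards no difference.** That holds for the risk difference and the test when capture is equal. The expected risk ratio is unaffected, and unequal capture can bias either way.
- **A reader might picture patients leaving follow-up at some early clinic visit, or a review blind to all outside records.** The documents give no visit schedule and do not say which outside records can be seen. How often events are missed is unknown.
- **A reader might want only patients with a contact on or after day 90 to count as event-free in the primary rate.** That brings its own bias, because patients with complications are likelier to have a late contact. With 1 event in 18 and 9 of the 17 event-free patients lacking a late contact, 1/18 = 5.6% becomes 1/9 = 11.1%.

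It is also fair to say that low power dominates at 18 per arm. In the assumed cases above, a non-significant result is likely even with perfect capture. Section 4.e.iv calls its figure a minimum, so the trial could be larger. Finally, the chart review could be meant to follow the last patient's day 90. That reading is reasonable, but it cannot be squared with a May 2023 analysis if enrolment runs through April.

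**Conclusion.** The point holds as a gap in outcome ascertainment, and it should be closed before the chart pull. The plan cannot show how many patients in each arm support its 90-day rates, and it leaves the handling of unknown status to be chosen after the data are seen.

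The size of any resulting bias cannot be stated, because the documents give no capture rate. Under equal capture, the shrinkage of the risk difference equals the share of events missed. The part that can be dated is the timeline: 28% to 42% of enrolment days fall too late for 90 days of follow-up by May 2023. As a share of patients, that figure assumes even accrual through April 2023. It is larger if charts are pulled before the analysis date, and smaller if recruitment finishes early. The p = 0.034 to 0.070 shift assumes 18 per arm and an uncorrected chi-square test.

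**What to change.** - **4.b.iii:** add the date of last chart contact of any kind.
- **4.b.iv and section 8:** state that charts are pulled after the last patient's day 90, and reconcile the timeline. For surgery on 30 April 2023 that means after 29 July 2023, which also moves the July 2023 manuscript steps.
- **4.e.ii:** keep the planned rates as the primary analysis and state how a patient with no entry is scored. Report by arm the number whose 90-day status is known, meaning a recorded event or a contact on or after day 90. Add one sensitivity analysis: either count unknowns as events in one arm and then in the other, or run a time-to-event analysis censored at last contact. Do not make the day-90-contact denominator the primary rate.
- **4.e.vi:** list as a limitation that a late contact does not fully exclude events treated elsewhere.

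The cost is one chart field, a few lines of analysis text and a later data pull, with no new visits. The bounds may be wide: 28% of 18 is about 5 patients, and counting 5 unknowns as events moves an arm's rate by 5/18 = 28 points. That is a reason to correct the timing first. The field must be collected at the chart pull, because section 7.c deletes the electronic files and removes identifiers when the study ends.
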